## 2) INTRODUCTION

The current study will use a systematic case series design to pilot a manualised intervention for individuals with a diagnosis of Functional Neurological Disorder (FND). The study will recruit 8 participants and measure their FND symptoms, psychological wellbeing and

satisfaction with the treatment package delivered. Baseline measures will be collected during a pre-treatment meeting. Intervention will involve 6-8, 1-hour sessions delivered online via videocall. The intervention will aim to improve body perception by getting participants to ‘tune into’ (pay attention to) their body using different methods and in different physical and emotional states. The study will assess whether the treatment package is acceptable to participants and feasible to deliver. The study will also gather preliminary data around any changes in FND symptoms and psychological wellbeing to see if the intervention has the potential to improve clinical outcomes.

It is expected that the intervention delivered will be feasible and acceptable to deliver and successful in reducing participants’ FND symptoms. If this is the case, it would benefit both the participants of the study and people with FND in the future.

### **3) BACKGROUND**

Functional Neurological disorder is a problem with the functioning of the nervous system and how the brain and body communicate with one another (Pick, Goldstein , Perez, & Nicholson, 2019). Individuals with FND often exhibit the subjective clinical features of neurological conditions (e.g., seizure, paralysis, movement disorders and cognitive dysfunction), but there are objective signs that the symptoms are not caused by neurological damage or disease. 10-20% of patients seen in neurology clinics have FND (Pick, Goldstein , Perez, & Nicholson, 2019). In addition to neurological symptoms, individuals with FND often experience associated symptoms such as memory difficulties, headache and fatigue, which are distressing and impact on social/occupational functioning. This affects overall quality of life (Pick, et al., 2020). Psychological adversities (e.g., stressful life events and interpersonal difficulties) are also important risk factors in FND. They are often associated with poorer quality of life, increased symptom severity and reduced resilience (Pick et al., 2019). As such, psychological therapy forms a key aspect of treatment in this area.

The exact mechanisms that underlie FND symptoms are not yet fully understood. There has been an increased emphasis on theories of emotion processing and interoceptive difficulties. It has been hypothesised that individuals with FND may experience a deficit in interoception which affects the integration of signals from the body and mind (Yogarajah, 2019). This causes problems with the identification stage of emotion regulation (Gross, 2015). This combination of emotion processing and interoceptive deficit contributes directly to the generation of FND symptoms. Support for this model of FND comes from studies that have found reduced interoceptive awareness in individuals with FND (Yogarajah, 2019). Additionally, individuals with FND frequently report difficulties in emotional functioning such as, anxiety, depression and affect dysregulation (Williams , Reuber, & Levita, 2020).

In addition to difficulties with emotion processing there is research on the relationship between dissociation and FND. Dissociation in FND refers to a range of phenomena such

as emotional numbing, memory and identity impairments as well as bodily symptoms. It is thought that individuals with FND may have a predisposition towards dissociation and this contributes (via impairments in interoception) to the generation and severity of FND symptoms (Pick, et al., 2020).

Current psychological models used to treat FND are Cognitive Behavioural Therapy (CBT), Psychodynamic therapies and hypnosis. These interventions usually focus on coping with the impact of FND symptoms and improving quality of life. Due to the growing body of evidence suggesting that individuals with FND struggle with interoception, emotion identification and dissociation there is the potential to develop new therapies that target these mechanisms directly. Additionally, there may be a resistance in individuals with FND towards psychological accounts of their symptoms (O'Connell, et al., 2020). Interventions targeting body perception may be more accepted due to an emphasis on physical and cognitive awareness. With that in mind, the current study aims to evaluate the acceptability, feasibility and efficacy of a 6-8 session treatment package designed to improve mind-body integration in individuals with FND.

The designed intervention is derived from the Integrative Cognitive Model (ICM) of medically unexplained symptoms and Psychogenic Non-Epileptic Seizures (Brown, 2004; Ven den Bergh, Witthoft, Petersen, & Brown, 2017; Brown & Reuber, 2016). This model suggests that conscious body perceptions are interpretations of bottom-up signals influenced by top-down factors such as attention, beliefs, fears and emotional states. The model suggests that Functional Neurological Disorders are distortions in body awareness that arise when normal bodily signals are misinterpreted as noxious, due to a combination of top-down factors and the bodily signals themselves being weak. The intervention targets several factors identified as important in this model, including imprecise bodily signals, poor emotion recognition and regulation, anxious beliefs and fears about symptoms and symptom-focussed processing. The intervention aims to sharpen signals from the body by reducing avoidance and misinterpretation of those signals and thereby improve body perception and interoceptive accuracy. If acceptable, feasible and effective, the intervention would contribute to the literature for the Integrative Cognitive Model of FND and inform future interventions for individuals with FND.

## **4) STUDY OBJECTIVES**

### **4.1 Primary Question/Objective:**

The primary aim of this study is to develop and begin testing the acceptability and feasibility of a 6-8 session treatment package aimed at improving mind-body integration in a series of people with FND. This will be measured using adherence to therapy, patient satisfaction and acceptability measures.

## **4.2 Secondary Question/Objective:**

The secondary aim is an initial evaluation of the efficacy of the piloted treatment package including impact on psychological distress, core FND Symptoms and quality of life.

## **5) STUDY DESIGN & PROTOCOL**

### **5.1 Participants**

Eight participants will be recruited for the current study from FND charities. Participants will be aged 18 and above with a diagnosis of Functional Neurological Disorder as evidenced by a letter from a medical doctor confirming the diagnosis. Recruitment involves the use of an equality and diversity strategy to maximise the chance of recruiting a sample that is ethnically diverse.

### **5.2 Study Intervention and/or Procedures**

Treatment:

- Participants will be offered 8, 1-hour, online sessions, delivered weekly via Microsoft Teams. The intervention will focus on developing skills to improve attunement to the signals from the body to the brain.
- The sessions will involve engaging in various exercises tuning into the body under different circumstances. Participants will be asked to tune into how particular objects feel in their hands. Participants may be presented with short clips or stories to make them feel a little happy or sad and then will be asked to tune into how the body feels in response to them.
- These sessions will be recorded via Microsoft Teams and selected aspects of them will be observed by the principal researcher and their clinical supervisor to ensure therapy quality.
- Participants will be asked to complete weekly measures online via Qualtrics survey platform in the 10-15 minutes prior to their session commencing. Assessment measures (CORE-10, FND symptoms questions, EuroQol Dimension and a measure of adverse reactions to the therapy) will be completed weekly. Any adverse reactions will be addressed in the beginning of the session.
- In the final session of treatment, all the preliminary measures will be repeated along with the measures of satisfaction in therapy and intervention acceptability.
- Following the final session of treatment, a date to complete a one-month follow up will be arranged with the participant.

Follow-Up:

- One month following the end of psychological therapy, a session will be attended remotely via Microsoft Teams by participants.

- During this session, all pre-treatment, weekly and post-treatment measures will be re-administered including questionnaires measuring satisfaction with therapy.

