- Participants meeting all criteria and having completed the safety plan will complete baseline measures: CORE 34, 5 questions assessing FND symptoms, the Screening for Somatoform Symptoms 7 (SOMS-7) and the Work and Social Adjustment Scale (WSAS).
- Following completion of baseline measures, the first remote session to deliver the psychological intervention will be arranged with the participant.

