## **11) SAFETY CONSIDERATIONS AND ADVERSE EVENTS**

The study is offering participants a novel treatment package focussing on improving the communication between body and brain through 6-8 sessions of psychological therapy. As with any novel psychological intervention, there is the potential that the intervention could cause an increase in symptoms or increase psychological distress. In order to protect participants from harm, adverse and serious adverse reactions will be monitored for all participants, including any changes in symptoms and risks to self or others. The research team will make every effort to prevent adverse reactions from happening. Further detail on the protocols is included in the Ethical Considerations section.

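### Reactions to the last therapy session are not systematically asked about until the one-month follow-up, because the adverse-reaction measure is taken only before each session

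*Combined protocol and SAP*

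**What the plan says.** Section 5.2 sets the treatment schedule: "Participants will be offered 8, 1-hour, online sessions, delivered weekly via Microsoft Teams". The Introduction gives a range instead: "Intervention will involve 6-8, 1-hour sessions delivered online via videocall".

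The weekly survey is completed on Qualtrics "in the 10-15 minutes prior to their session commencing". It contains the CORE-10, the FND symptom questions and, to finish the list, "EuroQol Dimension and a measure of adverse reactions to the therapy) will be completed weekly". Any reaction reported is then taken up at the start of that session.

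For the end of treatment, section 5.2 says: "In the final session of treatment, all the preliminary measures will be repeated along with the measures of satisfaction in therapy and intervention acceptability". Section 6.3 lists the baseline measures as "CORE 34, 5 questions assessing FND symptoms, the Screening for Somatoform Symptoms 7 (SOMS-7) and the Work and Social Adjustment Scale (WSAS"). That list has no adverse-reaction measure.

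The next scheduled contact is the follow-up: "One month following the end of psychological therapy, a session will be attended remotely via Microsoft Teams by participants". All pre-treatment, weekly and post-treatment measures are given again there, so the adverse-reaction measure returns at that visit.

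Section 9.1 names safety, in the form of adverse reactions, among the quantities that answer the primary aim, and plans a descriptive summary of adverse events. Section 11 acknowledges that "there is the potential that the intervention could cause an increase in symptoms or increase psychological distress".

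**The concern.** The survey before a given session looks back on the sessions already held. For every session but the last, another survey follows a week later. For the last session there is no further pre-session survey, and the battery given on that day is not described as asking about reactions. Even if it did ask, it could not pick up a reaction that appeared in the days afterwards.

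Two things are at stake. First, the adverse-event summary in section 9.1 would combine sessions asked about after one week with one session per participant asked about after about a month, without saying so. A reaction that came and went in the first days is more exposed to imperfect recall at a month than at a week. Second, the routine of asking about reactions and then addressing them at the next session has no counterpart after the last session, although section 11 recognises that symptoms or distress could increase.

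**Working it through.** The plan states no figure on this point, so there is none to reproduce. The check is a timeline.

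**Inputs**
- Sessions are weekly, 8 in number (section 5.2) or 6 to 8 (Introduction).
- The weekly survey, with the adverse-reaction measure, is taken just before each session (section 5.2).
- The final-session battery has no listed adverse-reaction measure (sections 5.2 and 6.3).
- The adverse-reaction measure is next given at one month (section 5.2).
- 8 participants are recruited, with at least 6 expected to complete (section 9.2).

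**Assumptions**
- Sessions are exactly 7 days apart, and one month is 28 to 30 days.
- The baseline measures in section 6.3 are what section 5.2 calls the preliminary measures.
- The satisfaction and acceptability instruments, which the protocol does not name, do not ask about adverse reactions.

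**Step 1: which sessions each survey can cover.** With S sessions on days 0, 7, ..., 7(S − 1), the survey before session k covers sessions 1 to k − 1. Survey 1 covers none, and survey S covers S − 1. With S = 8, the eight pre-session surveys cover seven sessions.

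**Step 2: delay from each session to the next survey with the adverse-reaction measure.**
- Sessions 1 to S − 1: 7 days.
- Session S: 28 to 30 days.
- Ratio: 28/7 = 4.0 to 30/7 = 4.3.

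**Step 3: share of sessions with the long delay (1/S).**

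| Sessions | Share | If 8 participants complete | If 6 complete |
|---|---|---|---|
| 8 | 1/8 = 12.5% | 8 of 64 | 6 of 48 |
| 7 | 1/7 = 14.3% | 8 of 56 | 6 of 42 |
| 6 | 1/6 = 16.7% | 8 of 48 | 6 of 36 |

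**Step 4: scheduled adverse-reaction assessments.** Strictly between the last session and the one-month visit there are none. Only one assessment can cover the whole course, the one-month visit itself.

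The two statements of session number differ, but the gap follows the last session whichever applies.

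**The case against.** The strongest reply is that safety is not left unattended in that month. Section 11 promises monitoring for all participants. Section 13.2 says that any event or reaction is logged, that a protocol manages risk for the duration of the study, that reactions go to clinical supervision, and that further support is discussed when the intervention ends. Section 6.3 provides a safety plan and a letter to the GP. Section 5.3 ends the study only after the last follow-up, so these arrangements run through the month in question. This stands: a reader might infer that reactions in that month would go unrecorded or unanswered, and the documents do not support that. The detailed risk protocol is also not part of the document, so it cannot be said to lack an interim contact. What the text does not set out is any scheduled asking, and a summary built on spontaneous reports for one session and a questionnaire for the others is not on equal terms.

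Three other stronger readings are tempting and should not be drawn.
- **That no survey ever covers the full course.** The one-month visit re-administers everything and does cover it, though later.
- **That efficacy has no measurement near the end of therapy.** The pre-session rule is stated for the weekly measures. The main battery is given in the final session, and its position within that session is not stated. It is a measurement at the end of therapy, and section 9.1 charts only the baseline and treatment phases. Whether to measure then or a week later is a design choice.
- **That a large part of the study lacks data.** About 4 of 7 + 4 = 11 weeks (36%) fall between the last session and follow-up, but this mainly restates that there is a one-month interval. One extra survey would still leave about 3 weeks empty.

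**Conclusion.** The point holds for the scheduled collection of adverse reactions, and only for that. As written, reactions to the last session are first systematically asked about roughly four times later than reactions to any other session. The size is one session per participant, 12.5% to 16.7% of sessions depending on course length. The person-session counts assume that completers attend every session. The protocol does not say what is collected from someone who stops early, so those participants are not counted here.

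The conclusion rests on weekly spacing, a month of 28 to 30 days, and a final-session battery without an adverse-reaction measure. That a longer interval weakens recall is a general argument; the documents give no figure for it. In a descriptive series of eight people no test result is at risk. This is a cheap improvement to one component of the primary aim, not a flaw that undermines the study.

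**What to change.** In section 5.2, add one further sending of the existing weekly Qualtrics survey, including the adverse-reaction measure, one week after the last session. In section 9.1, say that this survey contributes to the adverse-event summary.

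Keep the battery in the final session as the post-treatment time point for the RCI and CSC calculations, and leave the one-month follow-up unchanged. Moving the battery to an unsupervised link would risk losing that time point (each non-return is 1/8 = 12.5% of the participants), and using the in-session battery as a fallback would mix two time points under one label.

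The cost is one short survey per participant, about 8 in all, and a few words of text. Some may not be returned, so report how many were. The protocol should also say whether the extra survey counts towards the measure-completion rate in section 9.1 and the voucher bands in section 15. The bands are percentages, so the maximum payment stays at 8 × £45 = £360.

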#### **6.4 Participants who withdraw consent [or lose capacity to consent]:**

Participants are able to withdraw consent at any time without giving any reason as participation in the research is voluntary, without their care or legal rights being affected. If a participant wished to withdraw their consent, the principal researcher will request verbal consent for the data already collected to be used for the purposes of the project only and no further data will be collected. If the participant would like to withdraw their full consent, including any previous data collected for the purposes of the project, the principal researcher

will support this in withdrawing any data that has not yet been anonymised. Any data that has been anonymised will not be able to be withdrawn from the study.

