## **9.2 Sample Size:**

The appropriate sample size for a case series is variable depending on the type of study conducted and the depth of data yielded. Carey and Boden (2003), suggest that a case series can explore as few as two or three cases. This study will recruit 8 participants with a view to at least 6 participants completing the intervention. This ensures a larger sample than the minimum recommended in critical guides.

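### Participants who stop therapy early but still consent have no stated route to give satisfaction, acceptability or post-treatment data, so those results will tend to describe completers

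*Combined protocol and SAP*

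**What the plan says.** Section 4.1 says of the primary aim, acceptability and feasibility: "This will be measured using adherence to therapy, patient satisfaction and acceptability measures".

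Section 5.2 sets the timing of the measures:

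- Post-treatment set: "In the final session of treatment, all the preliminary measures will be repeated along with the measures of satisfaction in therapy and intervention acceptability".
- Weekly set (CORE-10, FND symptom questions, EuroQol and the adverse-reaction measure): "Participants will be asked to complete weekly measures online via Qualtrics survey platform in the 10-15 minutes prior to their session commencing".
- Follow-up: "Following the final session of treatment, a date to complete a one-month follow up will be arranged with the participant". At that remote session all measures are given again, including satisfaction.

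Section 6.3 lists the baseline measures: CORE-34, five FND symptom questions, SOMS-7 and WSAS. Of these, only the FND questions are also in the weekly set.

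Section 6.4 covers withdrawal of consent. The stated procedure is to "request verbal consent for the data already collected to be used for the purposes of the project only and no further data will be collected". It does not mention someone who stops therapy but is content to go on answering questionnaires.

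Section 9.1 plans descriptive statistics for the primary aim, and individual charts with reliable and clinically significant change for the secondary aim. It gives no denominator and no rule for missing data. Section 9.2 says: "This study will recruit 8 participants with a view to at least 6 participants completing the intervention".

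On safety, section 10 has adverse events and reactions recorded in the study master file. Section 11 commits to monitoring reactions in every participant. Section 13.2 has any event logged and documented.

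**The concern.** In a study whose main question is whether people find a therapy acceptable, those who leave are among the most informative participants. The plan expects that some may leave, since it recruits 8 and hopes for at least 6 completers. Section 13.2 also foresees that the team may withdraw treatment from participants, who need not have withdrawn consent.

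Two of the three components named in section 4.1 depend on reaching a final session, or a follow-up arranged from it. If leavers tend to be less satisfied or less improved, the reported satisfaction, acceptability and end-of-treatment change would look better than the experience of everyone who started. The completion rate would show that people left, but not why. With eight participants, two missing sets of answers cannot be recovered by analysis. They have to be sought at the time.

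**Working it through.** **Step 1. What an early leaver contributes under the plan as written.** Take someone who stops after session 3 and does not withdraw consent.

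| Item | Stated collection point | Available for this person? |
|---|---|---|
| Completion, sessions attended | Attendance records | Yes |
| CORE-10, FND questions, EuroQol | Before each session | Yes, up to session 3 |
| Adverse-reaction form | Before each session | Yes, up to session 3 |
| Adverse events recorded, logged and monitored (sections 10, 11, 13.2) | Not tied to sessions | Yes in principle; no method or time window after exit |
| Satisfaction, acceptability | Final session, follow-up | No stated route |
| Second SOMS-7, WSAS, CORE-34 | Final session, follow-up | No stated route |

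The weekly form is completed before the session starts. The leaver's last form therefore predates the last session attended, and a reaction to that session, including one that caused the exit, has no scheduled form.

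**Step 2. The plan's own figure.** Section 9.2 gives 8 recruited and at least 6 completing. The implied loss is 2/8 = 25%, and 6/(1 − 0.25) = 8. This check is circular, because the 25% is itself taken from 6 of 8. The plan gives no precision or power calculation to reproduce.

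**Step 3. Effect of missing answers on a reported proportion.** Let N = 8 starters, m = 2 without data, and k = favourable answers among the 6 completers. The completer figure is k/6. Over all starters the figure lies between k/N (both missing unfavourable) and (k + m)/N (both favourable).

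| k | Completers, k/6 | Worst case, k/8 | Best case, (k + 2)/8 |
|---|---|---|---|
| 6 | 100% | 75% | 100% |
| 5 | 83% | 62.5% | 87.5% |
| 4 | 67% | 50% | 75% |

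The width is always m/N = 2/8 = 25 percentage points. The same arithmetic applies to a count of reliable improvers on SOMS-7, WSAS or CORE-34. Six completers is an aim and not a floor. If 5 completed and all were satisfied, the worst case would be 5/8 = 62.5%; with 4, it would be 4/8 = 50%.

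**Step 4. How likely is at least one leaver?** The documents give no dropout rate, so a range is assumed, with participants independent: P = 1 − (1 − p)^8.

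- p = 0.10: 57%
- p = 0.20: 83%
- p = 0.25: 90%
- p = 0.30: 94%

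At any rate in this range, it is more likely than not that at least one person will leave early.

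**The case against.** A reader might infer that early leavers are missing from the safety answer, or that the whole primary result is completer-only. The documents do not support either reading. Leavers count directly in completion and attendance, and they report on the adverse-reaction form up to their last session. Sections 10, 11 and 13.2 commit to recording events and monitoring all participants, with no restriction to attenders. What stands on safety is the narrower gap in how reactions after exit would be found.

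A reader might also infer that all change results are completer-only. They are not. CORE-10, the FND questions and EuroQol are weekly, and section 9.1 charts each individual through treatment. Only the measures not in the weekly set lack a second score.

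The follow-up text speaks of participants and does not expressly exclude those who stopped. That is a fair point: the route is unstated and not closed. But the date is fixed after the final session, and nothing says how someone without one would be invited.

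Finally, section 9.1 states no denominator and the documents set no progression threshold, so the percentages above are illustrative and no formal decision turns on them. The exact 95% interval for 6/6 is 54% to 100%, which already contains 75%. This limits the consequence but does not remove the problem: that interval describes sampling variation, while selective non-collection shifts the result in one likely direction. Stopping data collection when consent is withdrawn is proper and is not criticised here. The consent form is not in the public copy, so its wording cannot be judged.

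**Conclusion.** The point holds for satisfaction, acceptability and the repeat of SOMS-7, WSAS and CORE-34. Participants who stop early but still consent have no stated route to give these data, so the results will tend to describe completers. Favourable bias is probable but not certain; it rests on the assumption that leavers are on average less satisfied or less improved.

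At the plan's own aim of 6 of 8 completing, the all-starter figure for any of these outcomes is uncertain by 25 percentage points. More than two losses would widen this.

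For safety, the gap is confined to the structured form being tied to sessions, with no stated method or window for finding reactions after early exit. No error in the sample size follows.

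The term final session is itself unsettled: sections 2, 4.1, 11 and 13.2 give 6-8 sessions, while section 5.2 offers 8. These passages must be reconciled before anyone can be classed as a completer or an early leaver.

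**What to change.** 1. **Section 5.2.** When a participant stops therapy early without withdrawing consent, promptly send the satisfaction, acceptability, adverse-reaction and post-treatment measures through the existing Qualtrics forms. Ask the reason for stopping, and keep the one-month follow-up invitation. State that returned adverse-reaction forms are reviewed by the team under the study's existing risk protocol, since no session will follow at which to raise them.
2. **Section 6.4.** Separate stopping therapy from withdrawing consent to further data, and make sure the consent form carries the same distinction.
3. **Section 9.1.** Report satisfaction, acceptability, and reliable and clinically significant change out of all participants who started treatment, with the number missing and best- and worst-case bounds. Show completers second. Do not make counting missing answers as dissatisfied or not improved the only result; that is just the worst-case bound.

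The cost is a short amendment using forms that already exist, plus a little extra form review. Some leavers will not reply, and the headline percentages may be slightly less favourable.
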